## Appendix 2: POISED intervention Chronic Disease-Specific Care Management Guides: Dementia and Diabetes

### CARE MANAGEMENT MATTERS

#### ***The basics:***

Following a prescribed diet plan, monitoring blood sugar regularly, using medications correctly, keeping a daily log, recognizing when diabetes is getting out of control, and keeping communication open with the medical team to respond to problems – all are important for successful management of diabetes. Team-based care management can help assure that caregivers have the support they need to accomplish these tasks. Care managers can also spot trends that indicate that a problem may require caregiver coaching, or more intensive medical care.

#### ***Know how dementia affects diabetes:***

- People with dementia may have problems with eating and drinking properly, and this can make diabetes harder to control. Problems can include under-eating, overeating, eating too few different foods, eating things that are not foods, and refusing to eat or drink fluids.
- Dementia may alter activity (exercise) patterns – higher or lower levels of activity may occur and can affect diabetes management.
- People with dementia need help managing medications. When dementia is mild, sometimes it's enough for a family member to watch over a loved one's self care, or help organize a schedule and make sure the log is completed accurately to monitor food, fluids, testing, and medications. Caregivers need to look for warning signs that more help is needed – since most people with *any* level of dementia benefit from more active help from family caregivers. In many cases caregivers will need to take over all aspects of diabetes care, and some will need coaching to assure that the person with dementia allows this transition to happen.

#### ***Understand how diabetes affects dementia:***

Big fluctuations in blood sugar – either too high or too low – cause people with dementia to have more trouble with confusion and erratic behavior, and reduce their ability to function. Long periods of poor control of blood sugar can lead to long-term, permanent worsening in brain function. Assuring good control of diabetes gives people the best chance to live well with dementia and diabetes.

#### ***Make and monitor a plan for everyday home care and caregiver coaching:***

##### MANAGING FOOD AND FLUID INTAKE

- Know the individual's prescribed diet. Identify and problem solve any specific difficulties patients and caregivers have in understanding or following it.
- Record food and fluid intake on a log. This helps avoid blood sugar that is too low (hypoglycemia) or too high (hyperglycemia).
- Record weight on a log, and note trends over time.

##### TESTING BLOOD SUGAR AND GIVING MEDICATIONS

- Know how to use the blood sugar meter and the blood sugar log ('daily glucose tracker').
  - Know how often to test and record blood sugar levels.

- Know when and how to adjust medication (if home adjustments are prescribed by the doctor).
- Take time to prepare the person with dementia before each test and each time medication is to be given – don't assume he remembers why this is important or what is happening.
- Identify caregivers who need coaching with any of these steps. Some caregivers may have trouble learning what to do, keeping on track, or approaching the person with dementia in a way that ensures cooperation.

**Red flags:**

- **Blood sugar readings below 80 mg/dl**
- **Sweating and shakiness (early warnings of hypoglycemia)**
- **Weight loss or gain of 5 or more pounds**

***People with dementia may not notice or tell you about these symptoms.***

***Tips for smarter caregiving:***

**Giving medication:**

- People with dementia may forget to take their medication.
- They are also at risk of taking too much medication because they forgot they already did. Medication boxes (MediSets) and blister packs help for medications given by mouth.
- Caregivers should use a log or calendar to check off when medications are given (caregivers get busy).
- All medications and over-the-counter medications should be kept safely out of reach to reduce the chance of mistakes.
- Some people with dementia may resist taking medications or have trouble swallowing. Ask the doctor about crushing the oral medication or disguising in food like pudding that the person will accept.
- Insulin injections: easiest when the routine is the same as before cognitive impairment developed, as long as this is medically recommended.

**Exercise:**

- Provide a predictable, regular, and pleasurable routine for daily exercise and rest (for the caregiver too!).

**Eating and food preparation:**

- When feeding becomes a problem, break it down:
  - Is lighting adequate in the dining area?
  - Is it quiet or is light music helpful?
  - Is the type and amount of social interaction conducive to eating? Some people may prefer to eat alone.
  - Is the person distracted by conversation, TV or radio, noise in another room?
  - Is there enough time allowed to chew and swallow?
  - Are foods the proper size?
    - Chop foods small enough to grasp, chew and swallow.
    - Puree foods when whole foods are not possible to eat due to the inability to chew or lack of teeth.
  - People who put food in their mouths and forget to swallow may be cued by gently stroking the sides of their neck.

- Caregivers should be taught the Heimlich maneuver to assist a choking person.
- Foam handles on utensils can facilitate grasping.
- For people who cannot use a spoon, a cup may be used to drink soup.
- Rubberized placemats may help to keep the food plate from slipping
- Are the food items distinguishable on a white or lightly colored plain plate. (People with dementia may not be able to distinguish food items from decorations embedded in the plate). A plain plate with dividers (as in a child's plate) may be helpful by separating foods and providing a "wall" against which foods may be pushed.
- Is the food at a reasonable temperature (not too hot or too cold)?
- People with severe dementia may "forget" how to eat. These people may be able to be coaxed by "following the leader."
- Dental disease, gum inflammation or soreness, mal-fitting dentures may interfere with eating.
- Visual impairment may impede eating. (Check that eye glasses are clean and in place)
- Constipation or bladder fullness may cause diminished eating.
  - Offer fluids every 2 hours; offer the bathroom an hour later.
  - Offer the bathroom  $\frac{1}{2}$  hour after eating a meal.
  - Acute refusal may indicate the need to defecate or void. Clues to this are resistance to sitting at the table or tugging at clothes.
- Because of amnesia associated with dementia, people may forget they have just eaten and request more food.
- Provide a standard and predictable routine for eating meals.
- Food preparation is a process that may require too many steps for a person with dementia living alone. An intermittent caregiver can prepare foods that are easy to open and do not require preparation. Consider home-delivered meals that do not require refrigeration or heating.

***Working with the doctor:***

- Caregivers need to know when to contact the doctor. Schedule a conversation to get those questions answered. Provide caregivers with a card they can post in a prominent place, with red flags, warning signs, and information about when and whom to call.
- Examples:
  - No bowel movement in 3-5 days signals a potential problem with constipation and should be brought to the attention of the doctor. Be sure to provide the food and intake log to the doctor.
  - If the person seems apathetic or sleepy, tell the doctor. Toxicity from too many medications or certain medications may lead to apathy or sedation. Bring the full up-to-date list of medications (including additional herbs and over-the-counter medications) to the doctor.
- Have a plan that all caregivers know about, including part-time and intermittent caregivers.
- Work with the doctor to simplify routines and medication plans.
- For every doctor visit: Bring a written list of caregiver's concerns, the full up-to-date list of medications (prescriptions, over the counter, supplements, and herbal medications) daily glucose tracker, and food and fluid intake and weight logs.

## Appendix 3: POISED Research Evaluation Survey

# POISED STUDY RESEARCH EVALUATION SURVEY

### SURVEY OVERVIEW

#### Notes to IRB:

*The POISED Study research evaluation survey is the baseline evaluation survey that will be modified for follow-up surveys. Text will be adjusted to orient the respondent to the follow-up survey time frames (3 months and 6 months). Also, demographic characteristic questions will not be repeated.]*

*The study research assistant will administer the baseline survey either in person at the Emergency Department visit if is practical and feasible without disrupting patient care as delivered by ED and hospital staff, or at a time by telephone that is agreeable to the caregiver.*

*The research assistant will administer the follow-up surveys by telephone.*

#### FOR TELEPHONE:

- Hello, my name is [*interviewer name*] from the POISED study. May I speak with [*Insert name of caregiver*]?

**\*\*Caregiver comes to telephone\*\***

- Hello, my name is [*interviewer name*]. I am from the POISED research study. You may remember that you spoke with me
  - when we did [*the consent*] or [*the other survey about 3 months ago (if this is a follow-up survey)*].
- I am calling you as part of the evaluation of this research study.
- Is it okay if we talk now?

#### INSTRUCTIONS TO INTERVIEWER:

If 'No', ask about another time that is more convenient.

If the person refuses to participate in the survey interview, thank the person.

If 'Yes', continue...→

- The program looks at ways to improve care for people with memory or thinking problems. The program is also for those family members or friends who provide help to the person with memory problems. We refer to individuals who provide help as caregivers or care

partners.

- Your participation in the program and interview will help us understand how best to help people with memory loss. Your participation will also help us understand how to help caregivers or care partners.

**Introduce Survey:**

- The interview will take about 30 minutes to complete. We will keep all of your answers confidential. Participating in this telephone interview is completely voluntary.
- If you feel uncomfortable answering specific questions, you can refuse to answer any or all questions. You may stop the interview at any time and continue it later. You may end the interview at any time and not continue.
- At the end of this interview, we will mail you a \$40 gift card for your time.
- Your decision to participate does not in any way affect the health care that either you or *[name of Care Recipient]* receives. None of the doctors that you or *[name of Care Recipient]* see will know whether or not you have participated in this survey.
- Do you have any questions about the study or about your participation?"

**IF YES: RESPOND TO ALL QUESTIONS BEFORE PROCEEDING.**

**Now I'm going to ask you a few questions to make this call as easy as possible.**

1a. Are you in a quiet and comfortable location?

Yes

No (wait for respondent)

1b. Am I speaking loudly and clearly enough for you to understand me?

Yes

No (go to 1c)

1c. (INTERVIEWER SPEAKING LOUDER) is this better?

Yes

No (code Hearing Impaired)

[If "No," thank the subject and end the interview explaining that you cannot conduct the interview because of difficulty hearing on the telephone. Immediately Contact the Program Coordinator. If the interviewer thinks the difficulty hearing is because of a bad connection (due to cell phone) offer to call at another time.]

**May I start the interview?**

No/Refused ➔ End Interview: Thanks very much for listening. Goodbye.

[REASON:  
\_\_\_\_\_]

## GENERAL QUESTIONS

**First, I would like to start this interview by asking you some brief general questions about yourself.**

1. How old are you today? \_\_\_\_\_ years old
2. What is your gender?  Male  Female
3. What is your race/ethnicity? You may answer yes to more than one.  
 White  Black  Asian  
 Hispanic  Other
4. What is your highest level of education?  
 Less than high school  Completed High school  
 Some college  College graduate+
5. What is your relationship to [name of Care Recipient], your Care Recipient?  
 Spouse  Child  
 Other relative  Friend/other
6. How many years have you been his/her caregiver? \_\_\_\_\_ years
7. What is your marital status?  
 Single/never married  Married  
 Divorced
8. What are your current living arrangements?  
 Live with Care Recipient  
 Live in close proximity How many miles? \_\_\_\_\_ miles  
 Other (please specify: \_\_\_\_\_)
9. How hard is it for you to pay for the very basics like food, housing, medical care, and heating?  
Would you say it is...  
 Very hard  
 Somewhat hard  
 Not hard at all

**Financial Strain:** Study of Women's Health across the Nation (SWAN) and the Coronary Artery Risk Development in Young Adults (CARDIA) studies (see, for example, Hall et al. [2009] and Puterman et al. [2013])

**Now I am going to ask you some questions about [insert name of Care Recipient], the person you care for.**

1. Where does he/she live? (ex. private home, assisted living, nursing home, other?)  
 Apartment/home/condo  
 Assisted living/ Board and Care  
 Nursing home  
 Other (please specify: \_\_\_\_\_)

2. Has [name of Care Recipient] ever received a diagnosis of dementia?  
 Yes     No
3. If Yes,  
About what year did he/she receive that diagnosis? \_\_\_\_\_  
Or, about how many years ago? \_\_\_\_\_
4. Has [insert name of Care Recipient] had a change in his/her primary care provider in the last year?  Yes     No
5. Does [insert name of Care Recipient] have health care insurance?  Yes     No
6. We have to ask for our study whether [insert name of Care Recipient] has a history of substance abuse, including alcohol?  
 Yes     No     Don't know/refused
7. Does he/she currently have a substance abuse problem?  
 Yes     No     Don't know/refused
8. Has [insert name of Care Recipient] received a diagnosis of any of the following conditions:  
 Depression     PTSD     Schizophrenia  
 Other (please specify: \_\_\_\_\_)

**Now I will ask you a few questions about traveling.**

9. We have [insert name of Care Recipient] address as [Fill In]. Is this correct?
10. What is the primary mode of transportation you use?

 Personal car	 Taxi
 Train	 Bus
 Walk	 Other ( please specify: _____)
11. Where do you go when you have to bring [insert name of Care Recipient] to see the doctor, meaning the doctor's office or clinic (usual source of care – USC) ? Do you have the location or address? \_\_\_\_\_
12. Where do you usually go if you need to travel to the hospital or Emergency Department (ED)? \_\_\_\_\_

*(For Calculating Miles and Difference in distance between ED vs. USC)*

**Next, I want you to think about the last 12 MONTHS and the care you have provided to [insert name of Care Recipient]. It might help to get a calendar.**

NOTE: FOR FOLLOW-UP SURVEYS, REPLACE "12 MONTHS" WITH THE CORRESPONDING TIME FRAME SUCH AS 3 MONTHS, 6 MONTHS

1. How many times did [insert name of Care Recipient], the person you care for, visit his/her Primary Care Provider or PCP in the last year? #\_\_\_\_ times
2. For each time, please indicate the primary reason for going to the PCP"

2a. Was the visit for a new symptom or for a change in a symptom that [insert name of Care Recipient]'s had previously?  Yes  No Acute use

2b. A fall or other injury?  Yes  No

2c. A symptom that has been present for more than the past month?  Yes  No Non-acute use

2d. A medication refill?  Yes  No

2e. Other (please specify: \_\_\_\_\_)

3. Have you had any difficulty getting medication refills for [insert name of Care Recipient]   
Yes  No
4. Over the past [insert time frame] has [care recipient name] had any new medical problems or illness?  Yes  No
5. Over the past [insert time frame] has [insert name of Care Recipient] had any injuries?   
Yes  No
6. How many times did he/she use the Emergency Department? #\_\_\_\_ times
7. How many times did he/she stay in the hospital overnight or longer in the last year? #\_\_\_\_ times

7a. For each stay in the hospital, I want you to tell me, to the best of your knowledge, the month and number of days he/she was in the hospital?

- i. Stay number 1: Month: \_\_\_\_\_. #\_\_\_\_ days
- ii. Stay number 2: Month: \_\_\_\_\_. #\_\_\_\_ days
- iii. Stay number 3: Month: \_\_\_\_\_. #\_\_\_\_ days
- iv. Stay number 4: Month: \_\_\_\_\_. #\_\_\_\_ days
- v. Stay number 5: Month: \_\_\_\_\_. #\_\_\_\_ days
- vi. Stay number 6: Month: \_\_\_\_\_. #\_\_\_\_ days

8. Over the past [insert time frame], has [name of CR] received help from the "In-Home Supportive Services" Program? This program helps pay for services to help keep [name of CR] safely in [his/her] home. Services include personal care and household tasks such as housecleaning, meal preparation, laundry, and grocery shopping.  
 Yes  No Non-acute use

8a. If Yes, how many months? \_\_\_\_\_

8b. How hours per week on average \_\_\_\_\_

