***Inclusion/Exclusion Criteria for Care Recipients:***

Inclusion criteria for participation in care management or usual care are as follows:

- 1) Must be 75 years and older
- 2) Must be in the emergency department for care at the point of recruitment
- 3) Must be English- or Spanish-speaking
- 4) Must have a family member or friend who provides caregiving assistance
- 5) Must have a plan to be discharged to home
- 6) Must have scored < 4 on the MiniCogTM15-19 or if using caregiver assessment by IQCODE, must be > 3.4
- 7) Must have capacity to consent or have a proxy.

Exclusion criteria for participation in care management or usual care are as follows:

- 1) Care recipient (CR) is a resident of a nursing home or other supportive facility
- 2) CR scores  $\geq 3$  on the MiniCogTM or the caregiver assessment by IQCODE was  $< 3.4$
- 3) Caregiver (CG) declines participation
- 4) CR is not being discharged to home

CR does not allow their family member or emergency contact to be contacted

Note: If the care recipient lacks capacity and we cannot obtain consent from their proxy, we will not access those data or include them in any analyses. Please note that a caregiver can still participate in the study with the assent of the care recipient, without the use of the health care data.

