*Usual Care Group:* The comparison group, those randomized to usual care (UC), will receive referrals to services at the time of enrollment. The usual care group will not receive the POISED structured assessment, attention to chronic disease management, or RCA related to the ED visit. Similar to intervention group, we will provide UC patients with a laminated card showing the Stress Thermometer™ (Appendix 5) for use in follow-up interview assessments.

**Specific Aim 1 Measures – Emergency Department (ED) Use:** We will obtain consent from patients to enable review of their medical records. We will identify all ED visits for the year prior to the index ED visit/study enrollment and for one year after enrollment. We will also search all-payer databases (APD) New York and the Indiana State Network for Patient Care to identify any episode of ambulatory or acute care that occurred within the 6 months of enrollment (6-month intervention and 6-month follow-up) and the 12 months prior to enrollment. Using the Care Recipient medical records, we will determine any prior diagnoses of dementia. We will also use the Care Recipient's medical records to determine comorbidity and root cause for ED use.

A one-item survey question will identify any additional visits that might have occurred outside the indicated state regions. For descriptive purposes, ICD discharge diagnoses will be included for any ED use. We will structure continuous variables that describe the number of ambulatory and/or acute care episodes.

**Aim 2: Develop a collaborative care plan with the interventional group and schedule follow up testing to assess whether the 6-month POISED intervention will improve family caregiver “activation” in managing the health care of care recipients compared with post-ED care without POISED at 3 and 6 months.**

*Strategy:* The POISED care management team consisting of specially-trained nurses functioning as care managers (CMs) and para-professionals in the role of care manager assistants (CMAs) will work to create an individualized care plan through the lens of cognitive impairment with an emphasis on coordinating care with the patient's primary care provider (PCP) and achieving relevance with the goals and capacity of the family CG and CR.

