#### Statistical Plan

We will compare randomization results to the pre-planned schedule, to ensure randomization integrity. To verify the comparability of the randomized groups, we will compare dyads to identify differences between their baseline characteristics (age, gender, race, education), CR comorbid medical conditions, and the Charlson comorbidity index. We will also look for differences in the number of primary care visits and acute care use during the year prior to enrollment between POISED and the usual care group by using analysis of covariance (ANCOVA) models for continuous variables and the Cochran-Mantel-Hansel statistic for categorical variables. We will control for stratification variables: recruitment site (NYU or IU), English vs Spanish (at NYU site), living arrangement (CG lives with CR or not), and cognitive status (Mini-CogTM score of a 3 or less). A cutoff of 0 or 1 is more strongly associated with functional disability than a cutoff of 3. Subjects requiring the IQ-CODE with scores  $>3.4$  will be included with those with MiniCogTM scores =0 to reflect greater impairment for those who cannot complete the Mini-CogTM. We will examine the distributions of continuous variables and use transformation or nonparametric methods in cases of violation to the normal distribution assumption. We will also examine the frequency distribution of all categorical variables and use exact inference procedures in cases of zero or small cell size. We will use SAS 9.4 (SAS Institute, Carey, North Carolina) for all analyses.

Specific Aim 1: We will use logistic regression models to compare the rates of ED admissions during the 6-month intervention period following the index (recruitment) ED visit. ED readmission within 6 months will be used as a binary outcome in the logistic model and randomization group will be the independent variable while adjusting for all stratifying variables including site, language, living arrangement and CR cognitive status. Baseline characteristics that are shown to be unbalanced in univariate comparisons between the two groups will also be adjusted.

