Sample Size and Power Consideration: Sample size for the proposed study is estimated for achieving 80% power in reducing acute care use in the POISED group compared with the usual care group in Specific Aim 1. A previous study had reported a 30-day readmission rate of 58% in dementia patients as compared to 38% in those without dementia. Given that our patient sample may include less severe cognitive impairment with less ED use, we assume, conservatively, that the rate of ED visits in the usual care group is 40%. With 320 patients enrolled per group, we will have 82% power to detect an odds ratio of 0.62 for repeat ED visits in the POISED group compared to the usual care group at the 0.05 significance level. This detectable odds ratio is equivalent to reducing the ED visit rate to 29% or lower in the POISED group compared with the 40% assumed for the control group. The use of stratified randomization ensures that patients in the intervention and control groups are similar on the stratification variables, thus reducing the variance of the difference between the two group means and resulting in greater power than simple randomization. Therefore, actual power for our study will be higher than projected here. Since we will be using EMR for acute care data and phone follow-up to supplement out of network use, we anticipate complete data from all study participants for this aim.

For Aims 2 and 3, assuming that 205 (64%) dyads will complete the 6-month evaluation (see Figure 2), we will have 80% power to detect an effect size of 0.28 or greater on the CG activation score, PHS-9, GAD-7 and MOS scores between POISED group and the control group using a two-sample t-test at the 0.05 significance level. The detectable effect size of 0.28 used in our power estimation is reasonable and justified given that previous studies on collaborative care management of dementia patients have shown an effect size of 0.45 SD on a number of caregiver psychosocial outcomes. Our previous studies have found a mean PHQ-9 score of 4.4 (SD=5.6), and a mean GAD-7 score of 3.2 (SD=3.5). Thus our projected effect size will allow us to detect a change as small as 1.6 on the PHQ-9 and 1 on the GAD-7. As described above, the use of stratified randomization will provide greater power than those projected here.

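### The only ED question printed in the caregiver survey asks for a bare count, so it cannot identify the out-of-state visits that Aim 1 relies on it to supply

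*Combined protocol and SAP*

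**What the plan says.** The Specific Aim 1 Measures section takes ED visits from the medical records, the New York all-payer database and the Indiana network. It then adds a survey source: "A one-item survey question will identify any additional visits that might have occurred outside the indicated state regions". The sample size section builds on this, citing EMR data and "phone follow-up to supplement out of network use, we anticipate complete data from all study participants for this aim".

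The survey in Appendix 3 contains one ED count, item 6 of the utilisation questions: "How many times did he/she use the Emergency Department", followed by a blank for a number. The follow-up note tells interviewers to replace the 12-month window "WITH THE CORRESPONDING TIME FRAME SUCH AS 3 MONTHS, 6 MONTHS". The survey overview also says that text will be adjusted to the follow-up time frames and that demographic questions will be dropped. It mentions no other change.

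Under Specific Aim 1 of the Statistical Plan, "ED readmission within 6 months will be used as a binary outcome in the logistic model", and the comparison covers events "during the 6-month intervention period following the index (recruitment) ED visit". Each care recipient has an index visit by design, because one inclusion criterion is "Must be in the emergency department for care at the point of recruitment".

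**The concern.** The survey question is there to find visits that the record sources cannot see. To do that it must show where and when a visit happened. A reported count of one could be an in-state visit already on file, an out-of-state visit, or the index visit itself.

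The index visit is the particular hazard. The recall window runs back 3 or 6 months from the call, so the index visit lies at its edge. A call made slightly early, or loose recall, brings it in, and nothing in the item tells the caregiver to leave it out. Because the outcome is any return visit, yes or no, one such report is enough to change a dyad's result.

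No section says how survey counts are reconciled with the records. The analyst can merge them and risk false events, or set them aside and lose the out-of-state supplement on which the expectation of complete data partly rests.

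**Working it through.** **What the item can and cannot separate**

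| Information needed | Item 6 | Elsewhere in the survey |
|---|---|---|
| Hospital or state of each visit | Not asked | Item 12 of the travel questions asks only which ED is usually used, to calculate distance |
| Date of each visit | Not asked; only a recall window | Item 7a asks month and days, but for overnight hospital stays |
| Exclusion of the index visit | Not stated | Not stated |

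Comparing totals does not settle it. Suppose the records show only the index visit and the caregiver reports one visit. If the caregiver meant the index visit, there is no event. If the caregiver left it out and meant an out-of-state visit, there is one. The two answers look the same.

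**The plan's own power figure**

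Inputs from the sample size section: 40% in usual care, odds ratio 0.62 (about 29% in POISED), 320 per group, significance level 0.05. I take the test as two-sided, which the section does not state.

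- Odds in POISED = 0.62 × 0.40/0.60 = 0.4133, so the rate is 0.4133/1.4133 = 29.2%.
- Power = Φ[(d − 1.96 × SE₀)/SE₁], where d is the difference in rates, SE₀ the pooled standard error and SE₁ the unpooled one.
- Result: 81.7% at 29.2%, and 83.5% at the rounded 29%. The stated 82% is reproduced.

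**Effect of counting index visits as events**

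Let f be the share of interviewed dyads with no true return whose caregiver reports the index visit and is counted as an event. Let r be the share interviewed. The observed rate is

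p′ = p + (1 − p) × r × f

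I set r = 0.64 in both arms, the completion expected at 6 months in the sample size section. True rates are 40% and 29%. The documents give no value for f, so a range is shown. For f = 10%:

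- Usual care: 0.40 + 0.60 × 0.64 × 0.10 = 0.4384
- POISED: 0.29 + 0.71 × 0.64 × 0.10 = 0.3354
- d = 0.1030, SE₀ = 0.0385, SE₁ = 0.0383 at 320 per arm
- Power = Φ[(0.1030 − 1.96 × 0.0385)/0.0383] = Φ(0.72) = 76%

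The protocol also gives a target of 900 dyads under Aim 1 in Methods. With equal allocation that is 900/2 = 450 per arm, so both sizes are shown.

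| f (assumed) | Observed rates | Odds ratio | Power, 320 per arm | Power, 450 per arm |
|---|---|---|---|---|
| 0% | 40.0% vs 29.0% | 0.61 | 83.5% | 93.6% |
| 2% | 40.8% vs 29.9% | 0.62 | 82% | 93% |
| 5% | 41.9% vs 31.3% | 0.63 | 80% | 91% |
| 10% | 43.8% vs 33.5% | 0.65 | 76% | 89% |
| 20% | 47.7% vs 38.1% | 0.68 | 69% | 83% |

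**The case against.** The best defence is that the records are the primary source and the survey only adds to them. The index visit takes place in a participating ED and its date is known, so a careful analyst could discount it. A survey count above the recorded total would at least flag an extra visit. ED revisits by care recipients are also reportable as adverse events. This stands in part: false events arise only if a survey count is allowed to override the records, and no section says that it is. But a flag does not show where or when a visit happened, and the plan does not link adverse event reports to the Aim 1 outcome.

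It is also fair to say that no section names item 6 as the one-item question, and that the printed form is the baseline version. The link is an inference, though item 6 is the only ED count printed and the promised follow-up changes concern time frames and dropped demographic questions.

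A reader might infer three stronger points, which the documents do not support:

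- *That follow-up counts reach back before enrolment*, because item 7 reads "How many times did he/she stay in the hospital overnight or longer in the last year" and item 1 uses the same period. The survey overview's general promise to adjust text to the follow-up time frames covers this, and neither item asks about ED visits.
- *That overlapping 3- and 6-month windows double-count events.* A visit reported twice leaves a yes/no outcome unchanged, and no section says that the counts are added.
- *That false events fall mainly on the POISED arm through higher interview completion.* The sample size section gives a single completion figure and nothing by arm.

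**Conclusion.** The point holds in a limited form. Used as printed, item 6 cannot identify out-of-state ED visits, so the plan's expectation of complete Aim 1 data lacks the support claimed for it. Whether it also creates false events depends on a merge rule that the plan does not state.

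If counts are merged and the error is equal in both arms, the effect is attenuation: a real benefit is harder to show, and a false benefit is not created. The loss is small at low error rates. At 320 per arm, power stays at about 80% with 5% misreporting and falls to 69% at 20%. At 450 per arm it stays above 80% throughout the range shown. The misreporting rates are assumptions, as is applying the 6-month completion figure to all survey reports, so the table illustrates the size of the problem and does not predict it. This should be corrected, but it does not undermine the design.

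**What to change.** In the 3- and 6-month surveys, replace item 6 with wording such as: *Since [index ED date / date of last interview], not counting the visit on [index date], how many times did he/she go to any Emergency Department?* For each visit, ask month, hospital and state.

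In the Statistical Plan, state that a survey-only visit counts toward Aim 1 only if it falls after the index visit, within 6 months of it, and outside the coverage of the record sources. Add a sensitivity analysis that uses the records alone. Name the follow-up item in the Specific Aim 1 Measures section so that the link is explicit.

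The cost is a survey amendment with IRB notification, and a minute or two more for caregivers who report a visit. No extra participants or staff are needed. The change is best made before follow-up interviews begin, since place and date cannot be recovered reliably afterwards.
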